9.3 Overlapping Toxicities

There is a possibility that hematologic toxicities and non-hematologic toxicities may overlap during study treatment. Overlapping toxicities will be monitored closely in both the Phase I and Phase II portions of the study.

9.4 Adverse Event Reporting

All Adverse Events (AE) will be recorded by the Investigator from the time of the start of study treatment through the end of the designated safety monitoring follow-up period (30 days after last dose of study treatment). AEs and study treatment administration must be recorded in the eCRF within 5 business days of awareness. All relevant historical medical conditions that are known/diagnosed prior to the administration of study drug(s) and ongoing at the time of study treatment initiation are to be recorded.

9.5 Abnormal Laboratory Values Defined as AEs

An abnormal laboratory value is considered to be an AE if the laboratory abnormality is characterized by any of the following:

- Results in discontinuation from the study
- Requires treatment, modification of study drug dose, or any other therapeutic intervention

- Is judged by the Investigator to be of significant clinical impact/importance
- Meets the criteria for a DLT as defined in Section 4.2.1.3

If a laboratory abnormality is one component of a diagnosis or syndrome, then only the diagnosis or syndrome should be recorded as an AE. If the laboratory abnormality was not a part of a diagnosis or syndrome, then the abnormality should be recorded as the AE.

9.6 Adverse Event Grading

CTCAE term (AE description) and grade: The descriptions and grading scales found in the revised NCI Common Terminology Criteria for Adverse Events (CTCAE) version 4.03 will be utilized for AE reporting.

Grade refers to the severity (intensity) of the AE:

CTCAEv4.03 Grade 1: mild; asymptomatic or mild symptoms; clinical or diagnostic observations only; intervention is not indicated.

CTCAEv4.03 Grade 2: moderate; minimal, local, or noninvasive intervention is indicated; limiting to age-appropriate instrumental activities of daily living (ADL; instrumental ADL refers to preparing meals, shopping for groceries or clothes, using the telephone, managing money, etc.).

CTCAEv4.03 Grade 3: severe or medically significant but not immediately life threatening; hospitalization or prolongation of hospitalization is indicated; disabling; limiting to self-care ADL (self-care ADL refers to bathing, dressing and undressing, feeding self, using the toilet, taking medications, and not bedridden).

CTCAEv4.03 Grade 4: life-threatening consequences; urgent intervention is indicated.

CTCAEv4.03 Grade 5: death due to an AE

9.7 Adverse Event Attribution

The Investigator will assess the relationship of the event to the study treatment. An adverse event is considered to be associated with the use of the study regimen if the attribution is determined as possible, probable or definite. The relationship assessment of the adverse event by the Investigator should be documented as follows:

- Unrelated: The AE is clearly NOT related to the treatment.
- Unlikely Related: The AE is doubtfully related to the treatment.
- Possibly Related: The AE may be related to the treatment.

- Probably Related: The AE is likely related to the treatment
- Definitely Related: The AE is clearly related to the treatment.

9.8 Communication between Investigational Sites

Investigational sites will be required to report AEs for all grades and attributions, SAEs, study drug administration, or any other problem that could affect the validity/integrity of the study data to the Sponsor-Investigator. Study drug administration issues or any other problem potentially affecting the validity/integrity of the study data should be communicated to the Sponsor by email or phone as soon as possible but within 2 business days of the Investigator learning of the event.

10 SAFETY DATA COLLECTION, RECORDING AND REPORTING

Safety variables include the following: AEs and SAEs (whether related to study treatment or not), laboratory changes, changes in vital signs and, in some instances, changes in images, as evaluated at the Investigator's discretion. Adverse events will be evaluated continuously throughout the study. Safety and tolerability, relationship to treatment and intensity will be assessed according to the Common Terminology Criteria for Adverse Events (CTCAE) version 4.03. All adverse events (Grades 1 – 5) will be determined by the Investigator and documented in subject study charts.

It is the responsibility of the Sponsor-Investigator, Investigators and the Protocol Team to ensure SAEs are reported according to the Code of Federal Regulations, Good Clinical Practices, the protocol guidelines, Institutional Review Board, and FDA policy.

10.1 SAE/Pregnancy and Lactation Reporting to Sponsor-Investigator

Upon learning of an event, Investigators/Investigational Sites must notify the Sponsor-Investigator of any SAE and pregnancy/lactation exposure within 1 business day of awareness from study treatment initiation through 30 days from the last dose of study treatment. All SAEs must be followed to resolution or to stabilization if improvement or resolution is not expected. SAEs that are determined to be related to study treatment or protocol-mandated procedures are reportable for the duration of the subject's participation in the trial. Each investigational site will be responsible to report SAEs that occur at their institution to their respective IRB in accordance with the IRB reporting policy.

When new significant information becomes available, a follow-up report must be reported to the Sponsor-Investigator within 1 business day of awareness.

10.2 SAE Reporting to the FDA

The Sponsor-Investigator will be responsible for all communications with the FDA. Upon learning of the event, the Sponsor-Investigator will report to the FDA, regardless of the site of

occurrence, any serious adverse event (SAE) that meets the FDA's criteria for expedited reporting following the reporting requirements and timelines in accordance with federal regulations.

Unexpected fatal or life-threatening experiences associated with the use of an investigational product will be reported to the FDA as soon as possible but in no event later than 7 calendar days after initial receipt of the information. All other serious, unexpected experiences associated with the use of the investigational product will be reported to the FDA as soon as possible but in no event later than 15 calendar days after initial receipt of the information.

The Sponsor-Investigator will notify any participating sites of SAEs reported to the FDA.

10.3 SAE Reporting by Sponsor-Investigator to Amgen and Incyte

The Sponsor-Investigator must notify Amgen regarding all SAEs occurring with carfilzomib. Subsequently, the Sponsor-Investigator must notify Incyte regarding all SAEs occurring with ruxolitinib. The MedWatch Form FDA 3500A must be completed for each event and the form must be sent to the respective funding company based on the contact information and reporting timelines listed below.

Note: Investigational sites are not responsible for submitting SAEs to funding companies as this is a sponsor responsibility.

The Sponsor-Investigator shall be responsible for collecting all SAEs and Pregnancy and Lactation Exposure Reports from all investigational sites and will exercise reasonable due diligence to obtain follow-up information from all investigational sites on incomplete SAE or Pregnancy and Lactation Exposure Reports. In the event that the funding company requires clarification or further information on individual SAE or Pregnancy and Lactation Exposure Reports, the funding company will not contact non-party investigators directly, but will route all such inquiries through Sponsor-Investigator for forwarding to such investigator(s). LCI will be responsible to ensure such inquiries are completed and provided to Amgen and Incyte in a timely manner.

Information not available at the time of the initial report (e.g., an end date for the SAE, discharge summaries, lot numbers, relevant laboratory values, scan data and autopsy reports) which are received after the initial report must be documented on a follow-up MedWatch and submitted to Amgen and Incyte. The Sponsor-Investigator will be responsible for obtaining follow-up information for the SAEs and demonstrate diligence in attempting to obtain such information from investigational sites by, among other things, maintaining written records of such attempts.

The Sponsor-Investigator will provide an annual IND report to Amgen and Incyte. Other reports containing safety data generated during the course of the study will be submitted to Amgen and

Incyte at the time the Sponsor-Investigator submits to anybody governing research conduct (i.e. regulatory authorities and IRBs). The Sponsor-Investigator will support reconciliation of all SAEs at the end of the study at a minimum.

10.3.1 Pregnancy Reporting to Amgen and Incyte

Sponsor-Investigator will report Pregnancy and potential infant exposure including Lactation to Amgen and Incyte within the timeframes listed below:

- Incyte: within 24 hours of Sponsor-Investigator awareness
- Amgen: within ten (10) calendar days of Sponsor-Investigator awareness.

10.4 Safety Reporting to the IRB

All events occurring during the conduct of a protocol and meeting the definition of an SAE will be reported to the central IRB per IRB requirements.

Protocol deviations will be reported promptly to the central IRB per IRB requirements.

11 DATA AND SAFETY MONITORING PLAN

Data will be collected in electronic case report forms (eCRFs). Study personnel will be trained on data entry by the sponsor and provided protocol-specific eCRF guidelines.

This protocol will be monitored according to the processes in effect for all Levine Cancer Institute Investigator- Initiated Trials and will abide by applicable regulations and guidelines (e.g. Good Clinical Practice [GCP]). It is the responsibility of the Sponsor-Investigator to monitor the safety data for this study. For the Phase I portion of the study, the Sponsor-Investigator, Statistician, and other study team members, as applicable, will conduct a teleconference after accrual of each cohort to review safety data before approving opening of subsequent cohorts for accrual. The Sponsor-Investigator, and other sponsor-level study team members, will meet to regularly to monitor subject consents, enrollment and retention, safety data and timeliness/validity/integrity of the data on a recurring basis. Documentation of recurring meetings will be kept in the study files. The Sponsor-Investigator will submit reports to the LCI Data and Safety Monitoring Committee according to the institutional LCI Data and Safety Monitoring Plan.

12 MEASUREMENT OF EFFECT

12.1 Timing of Response Evaluation

Response will be evaluated according to the schedule of evaluations listed on the Table of Events (Appendix [18.5](#))

12.2 Response Criteria:

The IMWG Response Criteria will be used for all evaluations of response. (Appendix [18.3](#))

12.3 Measurable Disease:

All subjects must have baseline assessment of disease that meet the criteria of measurable disease defined below:

- Serum M protein ≥ 0.5 g/dL (≥ 5 g/L) for IgG, IgA, or IgM disease, quantified by using densitometry on serum protein electrophoresis (SPEP).

AND / OR

- Urine M protein [Bence-Jones Protein] ≥ 200 mg/24 hrs (> 0.2 g/24 hrs), quantified by 24-hour urine protein electrophoresis (UPEP see Appendix III: Notes, h.).

OR

- Subjects who have both serum M protein levels < 0.5 g/dL AND urine M protein levels < 200 mg/24 hrs at baseline may be followed by serum free light chain (FLC) assay if involved free light chain level ≥ 10 mg/dL (≥ 100 mg/L).

13 STATISTICAL CONSIDERATIONS

13.1 Sample Size

13.1.1 Phase I

Phase I up to 18 subjects may be required to evaluate 3 dose levels of ruxolitinib in combination with carfilzomib and dexamethasone in a standard 3 + 3 design.

13.1.2 Phase II

Progression-free survival at 4 months is the primary endpoint for this study. The current study is investigating the impact of adding ruxolitinib to the combination of carfilzomib and dexamethasone in a carfilzomib refractory population. Published study results on carfilzomib plus dexamethasone in a carfilzomib refractory population (as defined in this protocol) have not

been identified. However, it is reported that the time on treatment in multiple myeloma patients receiving three or more lines of therapy had a median time on treatment of approximately 2 months²⁹. Therefore, it is assumed that if multiple myeloma subjects who are carfilzomib-refractory were retreated with carfilzomib plus low-dose dexamethasone, they would experience a median PFS of 2 months. A 2-month median PFS corresponds to a 4-month progression-free survival rate of 25%. In this patient population, if subjects treated with carfilzomib, ruxolitinib, and low-dose dexamethasone achieved a median PFS of 4 months, this would be considered a significant clinical benefit. A 4-month median PFS corresponds to a 4-month progression-free survival rate of 50%. A Simon's 2-stage design will be used to test the hypothesis that the 4-month PFS rate is less than or equal to 25%. Ten subjects will be enrolled in the first stage, and if at least 3 of the 10 subjects are alive and progression free at 4 months, an additional 20 subjects will be enrolled (a total of 30 subjects). If at least 11 of 30 subjects are alive and progression free at 4 months, the null hypothesis will be rejected (based on binomial probabilities). Assuming a one-sided alpha = 0.10 significance level, this sample size will provide at least 90% power to reject the null hypothesis, assuming the true 4-month PFS rate is 50%.

13.2 Endpoint Definitions

For response and progression-related endpoints, the baseline disease assessment will be the one that occurred prior to the start of ruxolitinib therapy.

13.2.1 Primary/Phase I: Dose Limiting Toxicity (DLT)

DLTs will be determined for each subject enrolled in Phase I as a binary variable indicating whether or not the subject experienced a DLT (as described in Section 4.2.1.3) during Cycle 1 of ruxolitinib treatment administration.

13.2.2 Primary/Phase II: 4-Month Progression-Free Survival

4-month progression-free survival (PFS4) will be determined for each subject as a binary variable indicating whether or not the subject is alive and progression free at 4 months. The timing of PFS4 begins at the time subjects start treatment with ruxolitinib. The criteria for progression are described in the IMWG Criteria (Appendix [18.3](#)).

13.2.3 Progression-Free Survival and Time to Progression

PFS is defined as the duration of time from the initiation of study treatment with ruxolitinib to first occurrence of either progressive disease or death. Disease progression as described by IMWG Criteria (Appendix [18.3](#)). The date of progressive disease is the date of the initial assessment that identified progressive disease. If the subject dies without documented disease progression, the date of progression will be the date of death. For surviving subjects who do not

have documented disease progression, PFS will be censored at the date of last disease assessment. For subjects who receive subsequent anti-cancer therapy prior to documented disease progression, PFS will be censored at the date of last disease assessment prior to the commencement of subsequent therapy. Subjects who have an initial PFS event immediately following 2 or more consecutive missed assessments will be censored at the date of the last assessment prior to those missed assessments. For subjects with only one missed assessment, the documented progressive disease status and assessment date will be used. Time to progression (TTP) will be determined in a similar fashion as PFS, with the only difference being TTP will be censored at the death date for subjects who die without progressive disease.

13.2.4 Overall Survival

Overall survival is defined as the duration from initiation of ruxolitinib treatment to the date of death from any cause. Subjects who are alive or lost to follow-up at the time of the analysis will be censored at the last known date they were alive.

13.2.5 Objective Response

Objective response will be determined for each subject as a binary variable indicating whether or not the subject achieved a best overall response of PR or better as per the IMWG criteria after initiating treatment with ruxolitinib.

13.2.6 Clinical Benefit

Clinical benefit will be determined for each subject as a binary variable indicating whether or not the subject achieved a best overall response of minimal response (MR) or better as determined by the IMWG criteria (MR adapted from EBMT) after initiating treatment with ruxolitinib.

13.2.7 Time to Best Response

This will be calculated for all subjects achieving an sCR, CR, VGPR or PR and separately for subjects achieving an MR and will be defined as the time from initiation of ruxolitinib treatment to the time of best objective status assessment of sCR/CR/VGPR/PR or of MR.

13.2.8 Disease control

Disease control will be determined for each subject as a binary variable indicating whether or not the subject achieved an sCR, CR, VGPR, PR, MR or SD \geq 8 weeks in duration after initiating treatment with ruxolitinib.

13.2.9 Duration of response

Duration of response will be calculated for all subjects achieving an sCR, CR, VGPR or PR and separately for subjects achieving an MR (defined per the EBMT criteria) and will be defined as the time from first objective status assessment of sCR/CR/VGPR/PR or of MR to the time of first documented disease progression or death. The censoring mechanism for duration of response will be the same as that described for PFS.

13.2.10 Safety Endpoints

Safety endpoints will include ruxolitinib treatment administration, AEs, SAEs, deaths while on study therapy, vital signs, ejection fraction (%), and selected quantitative laboratory determinations. Treatment administration will be determined for each subject in terms of cumulative dose administration and dose intensity of ruxolitinib (adjusting for dose delays and reductions). Additionally, the relative dose intensity will be calculated for each subject in terms of the actual dose intensity as a percent of the intended dose intensity.

Phase II: Adverse Events of Special Interest (AESI)

AESIs will be continuously monitored during the Phase II part of the study in subjects receiving ruxolitinib for the purposes of the pre-specified stopping rule described in Section 13.4.3. AESIs will be determined for each subject as a binary variable indicating whether or not the subject experienced a Grade 3/4/5 adverse event related to the ruxolitinib-containing regimen. AESIs will consist of the following CTCAE terms:

- Heart failure
- Pneumonia
- Dyspnea
- Peripheral edema
- Hypertension

13.3 Analysis Populations

For the Phase I part of the study, the dose escalation and MTD evaluation will be conducted on the population who initiate Cycle 1, Day 1 treatment, and who meet the DLT evaluable criteria as described in Section 4.3. For the Phase II part of the study, the PFS4 evaluable population will include all subjects who initiate treatment with ruxolitinib, have experienced a PFS event within 4 months from the start of ruxolitinib treatment, or have at least 4 months of follow up time from the start of ruxolitinib treatment. The primary efficacy analysis will be conducted on the PFS4 evaluable population. Response-evaluable population will include all subjects (both Phase I and Phase II) who have baseline evaluation, measurable disease, and initiate study

treatment followed by at least one efficacy measurement. All response endpoints will be conducted on the response-evaluable population.

All other efficacy and ruxolitinib safety analyses will be conducted on the population of subjects (both Phase I and Phase II) who initiate treatment with ruxolitinib. Additionally, an analysis will be conducted on safety data collected from Cycle 1 through the cycle prior to initiation of ruxolitinib treatment (for all Phase II subjects initiating Cycle 1 with carfilzomib plus dexamethasone).

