4 INVESTIGATIONAL PLAN

4.1 Milestone Date Definitions

Registration date: the date the subject signs the informed consent form.

Enrollment date: the date of initiation of study treatment on Cycle 1, Day 1. For the Phase I part of the study, this will be the date of initiation of treatment with carfilzomib, dexamethasone and ruxolitinib. For the Phase II part of the study, this is the date of initiation of treatment with carfilzomib and dexamethasone +/- ruxolitinib.

Treatment discontinuation date: the date the Investigator decides to discontinue the subject from study treatment.

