4.2.2 Phase II Design

Subjects in the Phase II/Run-in period will receive an initial cycle with carfilzomib at the twice weekly dose of 56mg/m² and dexamethasone. Following Cycle 1, a response assessment will be done. Subjects with a response of PR or better (“Responders”) will continue therapy with carfilzomib and dexamethasone. After these responding subjects subsequently progress, they will be treated with ruxolitinib (at the dose established in Phase 1) in combination with carfilzomib and dexamethasone. Subjects with a response of less than PR (“Non-responders”) will add ruxolitinib at the dose established in Phase I to carfilzomib and dexamethasone for all subsequent cycles. The cycle when ruxolitinib is added will be considered Cycle 1 (cycle numbers will start over). Disease evaluation assessment results should be available prior to dosing on Day 1 of each cycle of Phase II until initiation of ruxolitinib treatment (to ensure initiation of ruxolitinib occurs on Day 1 of a cycle).

Enrollment in the Phase II part of the study will be carried out in two stages. During the first stage, 10 PFS evaluable subjects (Section 13.3) will be enrolled. Enrollment and Stage 1 analysis of the first ten subjects on the three drugs (carfilzomib-ruxolitinib-dexamethasone) will be completed to determine if at least 3 of 10 subjects are alive and progression free at 4 months. If so, an additional 20 subjects will be enrolled (a total of 30 subjects) during the second stage. If at least 11 of 30 subjects are alive and progression free at 4 months, the null hypothesis will be rejected (based on binomial probabilities, see Section 13.1.2). The overall duration of the Phase II portion of the study is expected to be no longer than 24 months. For both Phase I and Phase II, subjects will be assessed for response after each cycle with confirmation of response according to IMWG response criteria regardless of dose level treated. Doses of each study drug may be interrupted or reduced in an attempt to manage toxicity.

Table 2: Phase II/Run-In Dosing^a

Drug	Dose	Route	Schedule	Cycle Length
------	------	-------	----------	--------------

Dexamethasone	40 mg ^b	PO	D1, 8, and 15 (Prior to carfilzomib)	28 days
Carfilzomib	56 mg/m ^{2c}	Intravenously (IV) over 30 minutes	D1, 2, 8, 9, 15, and 16	

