4.3 Subject Enrollment

Phase I

Enrolled subjects in Phase I will be DLT evaluable if they experience a DLT during Cycle 1 of treatment with the carfilzomib, ruxolitinib and dexamethasone regimen.

Enrolled subjects in Phase I who do **not** experience a DLT must meet all of the criteria below to be DLT evaluable:

- complete Cycle 1 of ruxolitinib therapy defined as followed
 - initiate Cycle 2, or
 - discontinue ruxolitinib therapy prior to Cycle 2 if the discontinuation date (as defined in Section 4.1) is on Cycle 1 Day 25 or later
- return no more than 20% of the number of ruxolitinib pills prescribed for Cycle 1 (while taking into account the actual length of Cycle 1)
- do not receive G-CSF or platelet transfusions during Cycle 1

Subjects who discontinue study treatment without experiencing a DLT and do not meet the DLT criteria as stated above will not be included in the 3+3 MTD evaluation but will be included in the overall analyses. Enrollment of new subjects to the current cohort will only be considered if there is less than the required number of DLT evaluable subjects to determine toxicity for the cohort. For example, of 3 subjects in a cohort, one withdraws due to disease progression, but 2 others have DLT, there is no need to continue enrollment to the given cohort as the MTD has already been exceeded. Alternatively, of 3 subjects in a cohort, one withdraws due to disease progression, but 2 others have not experienced a DLT, enrollment to the cohort will continue to fully evaluate the cohort with three DLT evaluable subjects).

Phase II

All enrolled subjects will remain in the intent to treat population. Enrollment to the Phase II part of the study will continue until the sample size requirements for the PFS4 evaluable population are achieved (Section 13.3).

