8.6 Follow-Up

Subjects who received ruxolitinib on study and discontinue therapy for reasons other than disease progression should continue to have standard of care disease assessments done until progression or start of subsequent therapy. At such time, follow-up or overall survival status will take place every three months +/- 7 days until death, lost to follow up, or until the criteria defined for the final analyses (Section 13.4.1) are reached. However, in the event the criteria for the final analysis are met, and there are subjects who have not yet been discontinued from study treatment, subjects in follow up will continue to be followed until all subjects have discontinued study treatment and completed the required 30 day safety monitoring period (Section 9.3). Follow-up beyond the safety monitoring period is only required for subjects who received ruxolitinib.

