8.7 Off-Study

Subjects will remain on study until the criteria for the final analysis have been met. Reasons a subject may be removed from the study early include, but are not limited to:

- Subject non-compliance with study participation, in the opinion of the investigator
- The subject or legal representative (such as a parent or legal guardian) withdraws study consent
- The subject is lost to follow-up
- Investigator's decision to withdraw the subject
- Subject death
- Early study termination

Subjects who do not receive ruxolitinib will be taken off study after completion of the safety monitoring period (Section 9.3)

When subjects are removed from the study, the reason for study removal and date the subject was removed should be documented.

Subjects that are Off Study will not participate in any study related procedures, including data collection. The study will be considered complete when one or more of the following conditions is met:

- All subjects have completed all study visits.

- All subjects have discontinued from the study.
- The IRB, LCI DSMC, Sponsor-Investigator or Amgen or Incyte discontinues the study because of safety considerations.
- The Sponsor-Investigator defines an administrative or clinical cut-off date.

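### Section 13.3 defines the response-evaluable population by the start of study treatment rather than of ruxolitinib, so its literal wording admits run-in-only subjects to response-rate denominators whose numerators they cannot enter

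*Combined protocol and SAP*

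**What the plan says.** Section 13.3 sets the entry rule in two parts: "Response-evaluable population will include all subjects (both Phase I and Phase II) who have baseline evaluation, measurable disease, and initiate study" and then "treatment followed by at least one efficacy measurement. All response endpoints will be conducted on the response-evaluable population". Ruxolitinib is not named in either part. The next paragraph of Section 13.3 does name it: the remaining efficacy analyses and the ruxolitinib safety analyses are "conducted on the population of subjects (both Phase I and Phase II) who initiate treatment with ruxolitinib". The PFS4 evaluable population in the same section also starts from ruxolitinib initiation.

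Section 4.1 equates Phase II enrollment with the start of study treatment and adds: "For the Phase II part of the study, this is the date of initiation of treatment with carfilzomib and dexamethasone +/- ruxolitinib". The run-in is therefore study treatment. Section 4.2.2 schedules a response assessment after run-in Cycle 1. Subjects in PR or better stay on the two drugs, and "After these responding subjects subsequently progress, they will be treated with ruxolitinib".

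The plan expects that some subjects will never reach ruxolitinib. Section 8.6 says "Follow-up beyond the safety monitoring period is only required for subjects who received ruxolitinib", and Section 8.7 gives such subjects their own off-study rule.

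Sections 13.2.5, 13.2.6 and 13.2.8 define objective response, clinical benefit and disease control as yes/no outcomes reached once ruxolitinib has begun. Section 1.2 sets these objectives for recipients of the three-drug combination. Section 13.2 takes the pre-ruxolitinib assessment as baseline for response endpoints. Section 8.3.1 and footnote k of the Table of Events (Appendix 18.5) say that subjects crossing over from the run-in get a new baseline.

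**The concern.** The denominator and the numerator of the response rates are keyed to different events. The denominator opens at the start of study treatment; the numerator opens at the start of ruxolitinib. A subject who has only the run-in satisfies the first and can never satisfy the second, even with a PR on carfilzomib-dexamethasone.

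The efficacy measurement has the same gap. It must follow study treatment, but nothing says it must follow ruxolitinib. A run-in assessment could literally qualify a crossover subject who was never assessed on ruxolitinib.

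Two analysts could thus build different denominators, one from the words of Section 13.3 and one from the intent visible elsewhere. In an open-label single-arm trial that choice is better fixed before the data are seen.

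**Working it through.** **Step 1. Does a run-in-only subject meet the literal rule?**

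| Condition in Section 13.3 | Run-in-only subject | Source |
|---|---|---|
| Baseline evaluation | Yes, at screening | 8.3.1 |
| Measurable disease | Yes, required at entry | 3.1.1, 12.3 |
| Starts study treatment | Yes, carfilzomib-dexamethasone | 4.1 |
| Later efficacy measurement | Yes, if assessed after Cycle 1 | 4.2.2 |
| Can be scored a success | No, outcome must follow ruxolitinib | 13.2.5, 13.2.6, 13.2.8 |

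One route is a run-in responder who dies or withdraws before progressing. Such a subject has, by definition, a post-Cycle 1 assessment.

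**Step 2. Are these subjects additional to the 30?** Section 4.3 says "Enrollment to the Phase II part of the study will continue until the sample size requirements for the PFS4 evaluable population are achieved", and Section 13.3 builds that population on ruxolitinib initiation. Run-in-only subjects therefore do not use up any of the 30 places; they are extra.

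**Step 3. The plan's own figure.** No sample-size or precision figure is given for the response endpoints. The only one is the PFS4 design in Section 13.1.2: continue with at least 3 of 10, reject with at least 11 of 30. The exact rejection probability is the sum over x = 3 to 10 of P(X1 = x) × P(X2 ≥ 11 − x), with X1 ~ Bin(10, p) and X2 ~ Bin(20, p).

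- p = 0.25: 0.0914, within the stated 0.10.
- p = 0.50: 0.9116, meeting the stated 90%.

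The stated figures reproduce. The response-evaluable population does not enter this calculation.

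**Step 4. Size of the denominator effect.** The documents give no counts, so everything here except the two ceilings is assumed. N = 18 + 30 = 48 adds the Phase I and Phase II maxima in Section 3.1, because Section 13.3 pools the phases. With k run-in-only subjects a rate is multiplied by N/(N + k). Intervals are 95% Clopper-Pearson, as in Section 13.4.2.2.

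| Assumed k | Objective response, 12 successes |
|---|---|
| 0 | 12/48 = 25.0% (13.6 to 39.6) |
| 1 | 12/49 = 24.5% |
| 3 | 12/51 = 23.5% |
| 6 | 12/54 = 22.2% (12.0 to 35.6) |

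An endpoint with a higher rate moves further in percentage points: an assumed disease control of 30/48 = 62.5% becomes 30/54 = 55.6% at k = 6. Every shifted estimate stays inside the interval at k = 0.

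**Step 5. Treated but unassessed subjects.** Requiring a post-treatment measurement removes m treated subjects and multiplies the rate by N/(N − m). At an assumed m = 4, 12/44 = 27.3%. A Phase I or direct-to-ruxolitinib subject who dies before any assessment is a PFS4 failure under Section 13.2.2 but drops out of the response rate. This works in the opposite direction to k: with k = 6 and m = 4 the result is 12/50 = 24.0%, so the two effects can partly hide each other.

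**The case against.** The strongest reply is that the intent is already clear. Section 1.2 restricts these objectives to triplet recipients. Section 13.2 fixes the baseline for response endpoints before ruxolitinib, and a subject who never starts ruxolitinib has no such baseline. Section 13.3 itself plans only a safety analysis of run-in data. On that reading the requirement for a baseline evaluation already excludes run-in-only subjects. This carries weight as evidence of intent. It does not settle the rule, because Section 13.3 leaves baseline evaluation undefined, run-in-only subjects do have a screening baseline, and the neighbouring definitions name ruxolitinib where this one does not.

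Three stronger readings are tempting and are not supported:

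- A reader might infer that the plan scores run-in-only subjects as treatment failures. No sentence says so; it follows only from combining the denominator and numerator definitions, and Sections 1.2 and 13.2 point the other way.
- A reader might infer that the plan keeps unassessed crossover subjects while dropping unassessed direct-entry subjects. The literal words allow this. But Sections 8.3.1 and 8.4.1 and footnotes k and u of Appendix 18.5 reset the baseline at crossover. For a Cycle 1 non-responder the run-in assessment would ordinarily become that baseline and not a later efficacy measurement. The asymmetry then largely disappears.
- A reader might conclude that an evaluable-subject denominator is itself wrong. Requiring measurable disease and a later assessment is a legitimate choice for a descriptive rate, and replacing it outright would be partly a preference.

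It is also fair to object that 48 is a sum of ceilings, and that subjects with prior carfilzomib at 56 mg/m² or more skip the run-in and cannot add to k.

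**Conclusion.** The inconsistency is real but limited. As worded, Section 13.3 admits assessed run-in-only subjects to the denominators for objective response, clinical benefit and disease control, against the stated objective and the pre-ruxolitinib baseline rules. It also fails to tie the qualifying efficacy measurement to ruxolitinib.

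The size cannot be known from the documents. Under the assumed 12/48, six run-in-only subjects lower the rate by 2.8 percentage points (25.0% to 22.2%) and one lowers it by 0.5 points; with none, the effect is zero. These are descriptive secondary rates with no test or stopping decision attached. A reader might infer that the primary result is exposed. It is not: PFS4 has its own ruxolitinib-based population, and its sample size, alpha and power are unchanged. The point merits correction because the remedy is nearly free and removes a later choice of denominator.

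**What to change.** In Section 13.3, define the response-evaluable population as subjects who (a) initiate ruxolitinib, (b) have a pre-ruxolitinib baseline, as in Section 13.2, showing measurable disease, and (c) have at least one efficacy measurement after ruxolitinib starts.

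As a supportive analysis, report the same three rates over all ruxolitinib-treated subjects, counting those with no assessment after ruxolitinib starts as non-responders. Early deaths and dropouts then cannot raise the rate unseen.

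The cost is a wording change and one extra descriptive table, with no new data collection. The supportive rates may be slightly lower than the main ones.
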